3 STUDY OBJECTIVES AND DESIGN

3.1 Hypothesis and study objectives

The overall aim of this study is to assess the safety of discontinuing statin therapy compared to continuing statin therapy in multimorbid elderly adults without clinical cardiovascular disease.

The primary objective is to compare a composite endpoint of major CV events and all-cause death between control and intervention group. We hypothesize that discontinuing statins does not result in shorter event-free survival. The non-inferiority margin is set at 5.2 weeks over a two year observation period (as justified under 5.1).

Secondary objectives are the comparison of all-cause death (including CV and non-CV deaths) and patient-centered outcomes between the two groups.

In the subsample of subjects undergoing assessment of subclinical atherosclerosis using CAC scoring and biomarker measurements, the primary aim is to determine if the risk of a composite outcome of CV events and all-cause mortality after statin discontinuation differs among those with higher burden of subclinical atherosclerosis, as funded by the Swiss National Science Foundation. We hypothesize that in participants with greater degrees of subclinical atherosclerosis, statin discontinuation might be associated with a higher risk of CV events and mortality, compared to statin continuation. Secondary objective in the subsample is to determine if the risk of CV events and mortality after statin discontinuation differs according to the baseline levels of previously validated blood biomarkers.

3.2 Primary and secondary endpoints

Schedule of assessment

Study Period	Screening & Baseline	Intervention period				After intervention period	
		3 months	12 months	24, 36, 48 months	End of intervention	+ 1 month from end of intervention	Yearly after end of intervention ⁴
Time	0						
Time window		+/- 4 weeks	+/- 12 weeks	+/- 12 weeks	+/- 12 weeks	- 8 weeks	+/- 12 weeks
Visit type	On-site / Call*	Call	Call	Call	Call	GP practice	Call
Patient Information	X						
In- /Exclusion Criteria	X						
Informed Consent	X						
Randomization	X						
Start intervention	X						
Demographic data and contact information	X						
Mediterranean diet adherence questionnaire	X						
PASE questionnaire	X						
Physical variables ¹	X						
Biological variables ¹	X						
FRAIL-scale	X						
6-CIT	X						
Medical history	X						
Statin and other lipid-lowering drug intake	X	X	X	X	X		X
Current medication	X	X	X	X	X		X
CV event		X	X	X	X		X
Death		X	X	X	X		X
EQ-5D (5) – incl. CEA	X	X	X	X	X		X
VNPRS (verbal numeric pain rating score)	X	X					
Falls ³	X	X	X				
SARC-F questionnaire	X		X	X	X		X
Girerd adherence scale	X		X	X	X		
Lipid level			X ²			X ⁵	
Blood sample for biobank	X ⁷		X ⁶				
SAEs	X	X	X	X	X		
Coronary artery calcium scoring in cardiac CT	X ⁷				X ⁸		

¹ collected retrospectively from medical records up to one year before baseline

² taken from a sub-sample at GP practices (if the corresponding consent is available), results remain blinded until end of intervention visit

³ self-reported from baseline to 12 months

⁴ up to 10 years after baseline, if patient consent to data collection after end of intervention visit

⁵ if available at GP practices

⁶ taken from a sub-sample at GP practices (if the corresponding consent is available)

⁷ performed in a sub-sample at selected participating sites (if the corresponding consent is available), results remain blinded until end of intervention visit

⁸ potentially performed in the sub-sample that underwent baseline cardiac CT scanning (funding pending)

*Baseline can be performed by phone if wished by patient

Primary endpoint (see schedule of assessment for time of acquisition):

The primary endpoint is a composite endpoint of major non-fatal CV events (non-fatal myocardial infarction, non-fatal ischemic stroke) and all-cause death over a follow-up period of 2 years. All-cause death (and not CV death only) is chosen to account for a possible shift from CV to other causes of death (such patterns were seen in two statin RCTs (8, 9)). The composite endpoint was selected to assess the net clinical benefit in this population with expected high mortality.

Secondary endpoints (see schedule of assessment for time of acquisition):

- Composite endpoint of all-cause death and major non-fatal CV events (non-fatal myocardial infarction, non-fatal ischemic stroke)
- Major CV events (CV death, non-fatal myocardial infarction and non-fatal ischemic stroke) as composite and components thereof
- Total CV events (CV death, non-fatal myocardial infarction, hospitalization for unstable angina, non-fatal ischemic stroke (including TIA) and arterial revascularization (coronary and peripheral urgent and non-urgent revascularization))
- Total composite events (all-cause death, non-fatal myocardial infarction, hospitalization for unstable angina, non-fatal ischemic stroke (including TIA) and arterial revascularization (coronary and peripheral urgent and non-urgent revascularization))
- All-cause death
- Non-CV death
- EQ-5D questionnaire: for general quality of life and possible future cost-effectiveness (44)
- Verbal numeric pain rating score (VNPRS): statin associated muscle symptoms (45, 46)
- Falls
- SARC-F questionnaire: muscle function and sarcopenia (47, 48)
- Girerd Medication adherence scale: general medication adherence

Safety endpoints:

Safety endpoints are collected as primary/secondary endpoints.

Other endpoints (see schedule of assessment for time of acquisition):

- Statin and other lipid-lowering drug intake
- Current medication: Drugs against high blood pressure, antiplatelet drugs, blood thinners, and drugs against diabetes
- After 12 months, blood samples are collected from a consecutive sub-sample of 100 subjects per group who remained in the assigned group (i.e., no change in treatment allocation recorded and no CV event). The lipid levels, collected for indirect assessment of statin intake of these blood samples, will remain blinded until the end of the trial. In this sub-sample, an additional blood sample is stored in the biobank of the University Hospital Bern for further, not yet specified, analyzes. The blood sampling is only done if the subject has given his/her separate consent for blood sampling. In addition, the biobank storage is only done if the subject has given his/her consent to the further use of samples.
- Additional lipid level measurements are collected at the end of the intervention period from GPs, if available.
- At the end of the intervention phase, repeat cardiac CT scan will be potentially performed in participants who underwent a baseline cardiac CT scan, depending on future funding. The CT scans are only done if the subject has given his/her consent for this procedure. The outcome will be annualized change of Agatston score with adjustment for baseline value.

Baseline factors

- Demographic data
- Physical variables: weight, size, BMI, systolic arterial blood pressure, diastolic arterial blood pressure
- Biological variables: lipid levels, creatinine, albumin, blood glucose; in subgroup with cardiac CT scan: lipoprotein(a), high-sensitivity C-reactive protein, NT-proBNP, troponin
- Medical history: Cardiovascular (family) history, cardiovascular surgery, cancer history, diabetes history
- Current medication: Drugs against high blood pressure, to regulate heart rate / rhythm or for heart failure, Antiplatelet drugs, blood thinners and drugs against diabetes
- Physical activity (Physical Activity Scale for the Elderly (PASE)) (49, 50)
- Nutrition status (Validated 14-items questionnaire of Mediterranean diet adherence) (51, 52)
- Questionnaire for frailty (FRAIL-Scale) (53, 54)
- Cognition (6-CIT) (55, 56)
- A subgroup of subjects at sites that participate to this part of the trial will undergo a baseline native ECG-gated CT scan of the entire heart on a multi-slice helical CT scanner. At the end of the intervention period, the images from the CT scans will be centrally assessed at the Department of Cardiology in the Inselspital (University Hospital of Bern) and used for semi-automated CAC scoring using the Agatston method.(57, 58)

3.3 Study design

The study is a multicenter, randomized, non-inferiority trial conducted in multiple hospitals in Switzerland. Study sites have been grouped into core and auxiliary sites according to their recruitment capacity. All sites with a recruitment goal of ≤ 90 participants over the entire recruitment period are called auxiliary sites, sites with more than 90 participants are core sites.

Study subjects are randomly assigned in a 1:1 ratio to either discontinue (intervention arm) or continue (control arm) statin therapy.

The study is open-labelled, with blinded outcome adjudication. Identification of potential outcome events is performed centrally by partially blinded study team members over the phone and by collecting medical records. Partially blinded means that the study team members assess the participant's outcome events over the phone without knowing the group assignment. However, they will know the group assignment retrospectively when assessing medication compliance. Then, a blinded clinical event committee (CEC) classifies suspected events for the primary and secondary clinical outcomes (see 8.1 for details).

The main risks of this study design are:

- a) Potential co-medication and co-interventions that could influence endpoints (see also chapter 4.5 for details). This is addressed by 1.) documenting these co-medications and co-interventions at each follow-up and 2.) accounting for co-medication and co-interventions in the statistical analysis.
- b) Cross-over from one group to the other. This is addressed by 1.) distributing flyers to participants, GPs, and pharmacists, explaining the rationale of the trial and the group allocation 2.) documenting medication adherence, 3.) repeatedly advising GPs that lipid levels of the intervention group participants should not be measured during the trial, and 4.) performing a statistical Per-Protocol (PP) analysis that accounts for cross-over appropriately.

3.4. Study intervention

In the intervention group, statin therapy will be stopped from the next scheduled intake after given informed consent onwards. Additional lipid-lowering medication lowering LDL cholesterol (i.e., ezetimibe, PCSK9 inhibitors, future novel lipid-lowering medications with lowering of LDL

cholesterol demonstrated in randomized trials) will also be stopped in the intervention group. The participant's GP and pharmacist (if applicable) will be informed about the study.

4 STUDY POPULATION AND STUDY PROCEDURES

4.1 Inclusion and exclusion criteria, justification of study population

See chapter 2 for justification of study population and chapter 5.1. for sample size calculation. The target sample size is 1'800 participants. This study also enrolls vulnerable patients that cannot themselves provide informed consent (see 4.2).

Inclusion criteria:

- ≥70 years of age
- Multimorbid with ≥2 coexistent chronic conditions (defined by ICD-10 codes) with an estimated duration of 6 months or more based on clinical decision, besides dyslipidemia treated by statins
- Taking a statin for ≥80% of the time during the year before baseline

Exclusion criteria:

1. Secondary prevention based on previous large statin trials, defined as:
 - History of myocardial infarction type 1² (NSTEMI/STEMI) OR
 - History of unstable angina, defined as ACS symptomatic at rest, crescendo or new-onset angina (CCS 2 or 3) without ECG or cardiac biomarker changes (based on available documents) OR
 - Stable angina pectoris with a documented ischemia on a stress test or with a significant coronary disease defined as a coronary stenosis >50% OR
 - History of percutaneous coronary intervention (balloon or stent) or coronary artery bypass graft OR
 - History of ischemic stroke OR¹
 - History of Transient Ischemic Attack, defined as transient neurological deficit without diffusion restriction in MRI OR
 - History of carotid revascularization (stent or bypass) OR
 - History of peripheral arterial disease requiring revascularization (stent or bypass; Fontaine IV)
2. Aortic disease that required a vascular repair or aortic aneurysm with a maximum diameter >5.5 cm (men) or >5.2 cm (women) based on available documents
3. Diagnosis of familial hypercholesterolemia based on Dutch lipid score ≥6 based on available documents (LDL-c, Family History, Personal History) (1)
4. Elevated risk of death within 3 months after baseline, defined as:
 - hospitalized patients planned for palliative care within 24h of admission OR
 - hospitalized patients with a Palliative Performance Scale (PPS) level <30% (based on situation at least 1 month before hospitalization), this corresponds to an estimated survival of 43% after 3 months (2); OR
 - patients with an advanced metastatic cancer prognosis of ≤20% survival rate within 1 year after baseline (based on an online tool: <https://cancersurvivalrates.com>)
5. Participation to a clinical trial with potential impact on the STREAM cardiovascular endpoints (based on clinical judgment)

The following additional exclusion criteria apply only for the performance of cardiac CT scans (subsample of 500 subjects):

¹ This exclusion criterion does not apply to clearly cardio-embolic causes for stroke, (e.g. due to atrial fibrillation)

² patients with a history of type 2 myocardial infarction are eligible for the trial unless there is a significant coronary disease defined as a coronary stenosis >50% or a history of revascularization with PCI (balloon or stent) or CABG.

1. Body measures exceeding the CT scanner limits (morbid obesity exceeding weight and diameter limits)
2. Cardiac implants with metallic interference, such as pacemaker and mechanical heart valves
3. Orthopedic hardware in the mid or lower thoracic spine
4. Inability to hold breath for 10 seconds

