Inclusion- / Exclusion Criteria	
Inclusion criteria:
 
 • ≥70 years of age • Multimorbid with ≥2 coexistent chronic conditions (defined by ICD-10 codes) with an estimated duration of 6 months or more based on clinical decision, besides dyslipidemia treated by statins • Taking a statin for ≥80% of the time during the year before baseline 
Exclusion criteria:
 
 1. Secondary prevention based on previous large statin trials, defined as: 
 • History of myocardial infarction type 1 (NSTEMI/STEMI) OR • History of unstable angina, defined as ACS symptomatic at rest, crescendo or new-onset angina (CCS 2 or 3) without ECG or cardiac biomarker changes (based on available documents) OR • Stable angina pectoris with a documented ischemia on a stress test or with a significant coronary disease defined as a coronary stenosis >50% OR • History of percutaneous coronary intervention (balloon or stent) or coronary artery bypass graft OR • History of ischemic stroke¹ OR • History of Transient Ischemic Attack, defined as transient neurological deficit without diffusion restriction in MRI OR • History of carotid revascularization (stent or bypass) OR • History of peripheral arterial disease requiring revascularization (stent or bypass; Fontaine IV) 2. Aortic disease that required a vascular repair or aortic aneurysm with a maximum diameter >5.5 cm (men) or >5.2 cm (women) based on available documents 3. Diagnosis of familial hypercholesterolemia based on Dutch lipid score ≥6 based on available documents (LDL-c, Family History, Personal History) (1) 4. Elevated risk of death within 3 months after baseline, defined as: 
 • hospitalized patients planned for palliative care within 24h of admission OR • hospitalized patients with a Palliative Performance Scale (PPS) level <30% (based on situation at least 1 month before hospitalization), this corresponds to an estimated survival of 43% after 3 months (2); OR • patients with an advanced metastatic cancer prognosis of ≤20% survival rate within 1 year after baseline (based on an online tool: https://cancersurvivalrates.com) 5. Participation to a clinical trial with potential impact on the STREAM cardiovascular endpoints (based on clinical judgment)

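### Exclusion criterion 1 leaves unstable angina with ECG changes but normal biomarkers in no exclusion line, and does not say how a TIA without MRI is classified

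*Protocol*

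**What the plan says.** Section 3.1 of the Protocol aims the trial at "multimorbid elderly adults without clinical cardiovascular disease". Section 4.1 puts this into practice through exclusion criterion 1, which opens with "Secondary prevention based on previous large statin trials, defined as" and then gives a list of histories joined by OR.

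The lines that matter here are:

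- Infarction: "History of myocardial infarction type 1 (NSTEMI/STEMI". Footnote 2 in section 4.1 keeps type 2 infarction eligible unless there is coronary stenosis above 50% or prior revascularisation.
- Unstable angina: "History of unstable angina, defined as ACS symptomatic at rest, crescendo or new-onset angina (CCS 2 or 3) without ECG or cardiac biomarker changes", judged on available documents. The synopsis repeats it: "crescendo or new-onset angina (CCS 2 or 3) without ECG or cardiac biomarker changes (based on available documents".
- Stable angina, if a stress test showed ischaemia or there is a coronary stenosis above 50%.
- Revascularisation: "History of percutaneous coronary intervention (balloon or stent) or coronary artery bypass graft".
- Ischaemic stroke, with footnote 1: "This exclusion criterion does not apply to clearly cardio-embolic causes for stroke, (e.g. due to atrial fibrillation".
- TIA: "History of Transient Ischemic Attack, defined as transient neurological deficit without diffusion restriction in MRI", again the same in the synopsis.

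The protocol does not say how to classify unstable angina with ECG changes and normal biomarkers, or a TIA diagnosed without MRI.

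**The concern.** Two of the definitions rest on a negative finding. The unstable-angina line asks for no ECG change and no biomarker change; the TIA line asks for no diffusion restriction. A definition of this kind works only if the neighbouring line takes everyone whose test was positive, and if the test was done in everyone.

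For unstable angina the first condition fails. The infarction line takes those who had an infarction, but not those who had ECG changes without one. For TIA the second condition may fail, because past events need not have been imaged by MRI.

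At stake is who the trial represents and who is asked to stop. The risk-benefit section (7.2) argues mainly from the absence of shown benefit in primary prevention. Allocation is 1:1 (section 3.3), so about half of those who enter through the gap would be assigned to stop the statin. Eligibility that depends on how a site parses a sentence also makes the recruited population less uniform across sites.

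**Working it through.** No formula applies and the plan gives no figure to reproduce. The check is a case-by-case reading of criterion 1 as written. It assumes that an episode with normal biomarkers is not recorded as a type 1 NSTEMI or STEMI; the protocol does not define infarction further.

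| History | Line that applies | Result |
|---|---|---|
| (a) Unstable angina, no ECG change, normal biomarkers | Unstable angina | Excluded |
| (b) Type 1 NSTEMI or STEMI | Infarction | Excluded |
| (c) Unstable angina, ECG changes, normal biomarkers, no PCI or bypass, no qualifying stable angina | None | Eligible |
| (d) As (c), but with PCI or bypass, or with qualifying stable angina | Revascularisation or stable angina | Excluded |
| (e) Transient deficit, MRI without diffusion restriction | TIA | Excluded |
| (f) Transient deficit, MRI with diffusion restriction | Ischaemic stroke, if classed as such | Excluded, subject to footnote 1 |
| (g) Transient deficit, no MRI done | TIA, depending on reading | Unclear |

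**Rows (a) to (d).** Rows (a) and (c) differ only in the ECG, and the patient with the abnormal ECG is the one who stays eligible. Two milder readings of the unstable-angina line were tried:

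- The qualifier only marks the border with infarction. The biomarker half would do that alone; the ECG half is what removes row (c) from the definition.
- The qualifier attaches only to new-onset angina. Rest and crescendo angina with ECG changes would then be excluded, but new-onset angina with ECG changes would still fall out.

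The gap narrows under the second reading but closes under neither. The stenosis threshold does not close it, because it sits in the stable-angina line. Footnote 2 shows that the authors did supply such a backstop for type 2 infarction.

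**Row (g).** If the wording requires an MRI that was negative, the patient is not excluded. If it means that no diffusion restriction was shown, the patient is excluded. The text supports both. The TIA line also lacks the reference to available documents that the unstable-angina line carries. Screening runs through hospital records, GP practices and possibly nursing homes and pharmacies (section 4.2), and baseline may be done by phone (schedule in section 3.2), so the imaging record may not always be at hand.

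**The case against.** The strongest reply is that both qualifiers are border markers: one separates unstable angina from infarction, the other TIA from stroke. A clinician would exclude row (c) without parsing the sentence, and section 4.2 gives study nurses physician supervision and phone access to study physicians at the main site. Other lines catch everyone with PCI or bypass and everyone with qualifying stable angina, which leaves mainly medically managed cases. The list also admits some vascular history on purpose, such as type 2 infarction and cardio-embolic stroke, so a vascular history among participants is not in itself an error.

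Most of this stands as a limit on size. It does not remove row (c): supervision helps only if someone sees the problem, and the written rule points the other way.

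A reader might infer four stronger things that the documents do not support:

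- **That TIA without MRI passes as primary prevention.** The wording is ambiguous and can equally be read as excluding these patients.
- **That footnote 1 lets patients in through the TIA line.** It exempts cardio-embolic stroke and not cardio-embolic TIA. That makes the TIA rule the stricter one and admits no TIA patient.
- **That the trial counts the same event as disease when it is an outcome but not when it is history.** Section 3.2 names hospitalisation for unstable angina and TIA within total CV events but gives no operational definitions. Classification lies with the clinical event committee, whose charter is not at hand.
- **That a given number of patients with established disease is affected.** The protocol offers no basis for any prevalence in the residual group.

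**Conclusion.** The concern holds for unstable angina as a gap in the written rule, and for TIA as an ambiguity. Followed exactly, criterion 1 admits a group that its own heading and the aim in section 3.1 mean to keep out. Because the unstable-angina wording is the same in the synopsis and section 4.1, it is not a slip in one place.

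The size is unknown and is probably confined to medically managed cases. No bias, loss of power or effect on the non-inferiority margin has been shown. The conclusion rests on reading the list as closed, which its opening words support, and on the assumption about how infarction is recorded. It is a correction worth making because a wrong classification bears directly on who is asked to stop treatment and the remedy is cheap.

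**What to change.** - Reconcile the unstable-angina and infarction lines in section 4.1 and the synopsis with the intent to exclude secondary prevention, so that no acute coronary presentation falls between them. The definitions are for the sponsor to choose.
- State how a diagnosed TIA is classified when no MRI was done, in both places.
- Check already randomised participants for these two histories where records allow. Use records from before randomisation, without knowledge of arm or outcome.
- Keep the intention-to-treat set of all randomised patients as planned, and add a sensitivity analysis of the primary endpoint without the participants so identified. Because the exclusion rests on baseline history and applies equally to both arms, the comparison stays a randomised one.

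The cost is a wording amendment, slightly fewer eligible patients and a limited query. The query may not settle every case: the baseline factors in section 3.2 cover cardiovascular history and surgery but do not list past ECG or MRI findings. The report should say how many histories could not be resolved.
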